5.4.2.1. Main Analytical Approach

All secondary endpoints will be analyzed using ITT population except for safety endpoints and PRO, which will be done using safety population.

.

All secondary endpoints in Section 5.4.2. will be summarized with descriptive statistics except for the endpoints referring to effectiveness and success (complete and qualified) .

These endpoints regarding complete/qualified success will be analyzed as follows:

For categorical secondary endpoints, the proportion of each treatment group will be computed and the 95% CI of difference between treatment groups will be computed using normal approximation.

For continuous secondary endpoints that is defined for one timepoint, the least squares mean change from baseline and the least squares mean difference between the treatment groups will be estimated using the analysis of covariance model with treatment as the factor, and baseline as a covariate variable. For continuous secondary endpoints that is defined for over time, the least squares mean change from baseline and the least squares mean difference between the treatment groups will be estimated using or mixed effects model repeated measure with treatment, time as the factor, treatment by time interaction and baseline as a covariate variable.

CONFIDENTIAL

Draft Statistical Analysis Plan v2.0

XEN-45 Gel Stent

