## **Methods of Statistical Analysis**

The number and proportion of subjects achieving  $\geq 20\%$  mean IOP reduction from baseline at Month 12 on the same or fewer number of topical IOP-lowering medications, without clinical hypotony, loss of vision to count fingers, or secondary glaucoma surgical intervention will be tabulated with 95% CI calculated by using the normal approximation method. The difference of the proportions will be estimated and the 95% CI of the difference will also be calculated with the method of the normal approximation. The 2 treatment groups will be claimed as equivalent if the 95% CI of the differences is within the -18% to 18% interval. The least squares mean change from baseline in IOP and the least squares mean difference between the 2 treatment groups will be estimated using the analysis of covariance (ANCOVA) model or the mixed-effect model repeat measurement (MMRM) model. The proportion and 95% CI of complete success and qualified success will be calculated with normal approximation.

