5.4.2. Secondary endpoints

All secondary endpoints will be analyzed using ITT population for efficacy and PROs.

Effectiveness:

CONFIDENTIAL

Draft Statistical Analysis Plan v2.0

XEN-45 Gel Stent

- Mean and changes in mean IOP from preoperative baseline over time
- Number of topical IOP-lowering medications from preoperative baseline over time
- Mean and changes in mean IOP and number of topical IOP-lowering medications from preoperative baseline over time in eyes with medicated baseline IOP ≤ 18 mm Hg
- Change in mean IOP from medicated baseline at Month 12
- Change in mean number of topical IOP-lowering medications from medicated baseline, at Month 12
- Proportion of participants with IOP value of ≤ 18 mmHg at Month 12
- Proportion of participants with IOP value of ≤ 17 mmHg at Month 12
- Proportion of participants with IOP value of ≤ 16 mmHg at Month 12
- Proportion of participants with IOP value of ≤ 15 mmHg at Month 12
- Proportion of participants with IOP value of ≤ 14 mmHg at Month 12
- Proportion of participants with IOP value of ≤ 13 mmHg at Month 12
- Proportion of participants with IOP value of ≤ 12 mmHg at Month 12
- Proportion of participants achieving $\geq 25\%$ IOP reduction from baseline at Month 12
- Proportion of participants achieving $\geq 30\%$ IOP reduction from baseline at Month 12
- Proportion of participants achieving $\geq 35\%$ IOP reduction from baseline at Month 12
- Proportion of participants achieving $\geq 40\%$ IOP reduction from baseline at Month 12
- Proportion of participants achieving $\geq 45\%$ IOP reduction from baseline at Month 12
- Proportion of participants achieving $\geq 50\%$ IOP reduction from baseline at Month 12
- Proportion of participants meeting all following criteria:
 - $\geq 20\%$ IOP reductions at Month 12
 - IOP value of ≤ 18 mmHg at Month 12
 - Same or lower in number of topical IOP-lowering medications at Month 12 compared to the baseline
- Proportion of participants meeting all following criteria:
 - $\geq 20\%$ IOP reductions at Month 12
 - IOP value of ≤ 17 mmHg at Month 12
 - Same or lower in number of topical IOP-lowering medications at Month 12 compared to the baseline
- Proportion of participants meeting all following criteria:
 - $\geq 20\%$ IOP reductions at Month 12
 - IOP value of ≤ 16 mmHg at Month 12
 - Same or lower in number of topical IOP-lowering medications at Month 12 compared to the baseline
- Proportion of participants meeting all following criteria:

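### The over-time MMRM fits one baseline slope to all eight postoperative visits; a baseline-by-time term would be a cheap, minor gain in precision

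*SAP*

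**What the plan says.** SAP 5.4.2.1 divides the continuous secondary endpoints in two.

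- "For continuous secondary endpoints that is defined for one timepoint", it prescribes an "analysis of covariance model with treatment as the factor, and baseline as a covariate variable".
- "For continuous secondary endpoints that is defined for over time", it prescribes a mixed model for repeated measures with treatment, time, "treatment by time interaction and baseline as a covariate variable". No interaction of baseline with time is listed.

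SAP 5.4.2 shows which endpoints fall where. The over-time group holds "Mean and changes in mean IOP from preoperative baseline over time", "Number of topical IOP-lowering medications from preoperative baseline over time", and the same two outcomes in eyes with medicated baseline IOP of 18 mm Hg or less. The single-timepoint group holds "Change in mean IOP from medicated baseline at Month 12" and the matching change in medication count.

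The protocol (Methods of Statistical Analysis) names only ANCOVA or a "mixed-effect model repeat measurement (MMRM) model" and gives no fixed effects. Neither document states the covariance structure or lists the visits that enter the model. Day 1 to Month 12, eight visits with four in the first month, is inferred from the schedule in SAP 1.2.

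The SAP paragraph also needs tidying. Its lead-in mentions only the success endpoints, and a stray conjunction precedes the mixed model. The ANCOVA/MMRM split is still the natural reading.

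**The concern.** A single baseline coefficient assumes that the preoperative value predicts the outcome equally well on Day 1 and at Month 12. After filtering surgery that may not hold. Protocol 8.4.5 lets topical drops be stopped 1 to 4 weeks before surgery and restarted at the investigator's discretion. Many eyes could therefore be drop-free early, with little link to baseline, and the link could return later.

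If slopes differ, the fitted common slope is a compromise. It over-adjusts at visits where the true slope is lower and under-adjusts where it is higher. Part of the baseline variation then stays in each visit's residual, and the treatment difference at that visit is estimated less precisely than the data allow. What is at stake is precision in the over-time tables of a trial now planned for 102 completers, 34 of them trabeculectomy eyes.

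**Working it through.** **The plan's own figure.** There is none to reproduce: the documents give no SD, slope or correlation for IOP or drop count. Everything below rests on assumed values, apart from the eight visits (SAP 1.2) and the 68/34 completers (SAP section 3).

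**Formulas.** Let b be the vector of true slopes at the eight visits, S the residual covariance across visits, SDx the baseline SD and SDres12 the Month 12 residual SD.

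- Common slope: bc = (1'S⁻¹b) / (1'S⁻¹1), a weighted average of the visit slopes.
- Month 12 variance ratio, common over visit-specific slope: VR = 1 + (b12 − bc)² × SDx² / SDres12².

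Analysing change instead of level lowers every slope by 1, so b12 − bc and VR do not alter. If all slopes are equal, b12 = bc and VR = 1.

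**Assumed slopes.** Zero through Month 1, one third of the Month 12 value at Month 3, two thirds at Month 6, full value at Months 9 and 12. Month 12 slope 0.2 or 0.5. Autoregressive correlation 0.5 or 0.7.

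**One case by hand.** IOP, residual SD 4 at all visits, SDx 5, correlation 0.5, b12 = 0.5.

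- Under this structure the first and last visits have weight 1 and the six between have weight 0.5 each, a total of 5.
- bc = [0.5 × (0.167 + 0.333 + 0.5) + 1 × 0.5] / 5 = 1.0 / 5 = 0.20.
- VR = 1 + (0.5 − 0.20)² × 25/16 = 1 + 0.09 × 1.5625 = 1.14.
- With b12 = 0.2, bc = 0.08 and VR = 1 + 0.12² × 1.5625 = 1.02.

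**Range over the scenarios.**

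| Outcome | Baseline SD | Residual SD, Day 1 to Month 12 | Month 12 variance increase |
|---|---|---|---|
| IOP | 5 | 5 falling to 4 | about 1% to 11% |
| IOP | 5 | 4 throughout | about 2% to 14% |
| Drop count | 1 | 0.2 rising to 1.1 | 3% to 20% |
| Drop count | 1 | 0.7 rising to 1.1 | 2% to 12% |
| Drop count | 1 | equal at all visits | 1% to 9% |

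On the SE scale, √1.14 = 1.07 and √1.20 = 1.10, so the upper ends are about 7% and 10%. The early visits lose too: for IOP, the variance at Day 1 to Month 1 is about 1% to 8% higher.

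**Who sets the slope.** With IOP residual SD falling from 5 to 4, the four visits to Month 1 carry about 40% of the weight and bc is about half of b12. With drop-count SD rising from 0.2 to 1.1, bc is 0.005 to 0.023, close to zero. With 0.7 rising to 1.1 it is about a quarter of b12. Over a wider set of variance and correlation assumptions for IOP, the early share runs from −0.24 to 1.05.

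**Stress test and simulation.** In that wider set the Month 12 slope goes up to 0.6, baseline SD is 4 or 6 and Month 12 residual SD is 4. The SE increase is 0.6% to 13% with equal residual variances and 0% to 6% with noisier early visits. It reaches 35% only in the extreme case of less variable early visits (SD 3), slope 0.6 and baseline SD 6. Simulations with 68/34 eyes, complete data and unstructured covariance gave SE ratios of 1.01, 1.03, 1.05 and, in that extreme case, 1.36. The mean treatment difference stayed within 0.02 mm Hg of its true value of zero.

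**The case against.** The strongest reply is that little of consequence depends on this model. The sentence just before the quoted one sends the named Month 12 change endpoints to an ANCOVA whose slope is fitted at Month 12 alone. The primary endpoint is a difference in proportions with no covariate mentioned (SAP 5.3.2). SAP 5.4.1 says that no secondary endpoint is key. All of this stands and limits the point to the over-time tables.

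It is also fair that the clinical premise has no source in the documents. No slope is given. Moreover, the default baseline is the preoperative visit (SAP 5.1), which may follow a stop of topical drops, so the assumed spread and slope for drop count may not survive. That stands too: the size is conditional.

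A reader might infer that the common slope is set mainly by the early postoperative visits, so that almost no baseline adjustment reaches Month 12. The documents do not support this. It depends on residual variances and a covariance structure that they do not state. For IOP with spread falling from 5 to 4 the early visits carry the smaller share, and for drop count the near-zero slope needs an assumed Day 1 SD of 0.2.

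What does not stand is that the point is only taste. The model as written has one slope, and the precision loss does not require early visits to dominate: with equal residual variances IOP still loses about 2% to 14% in variance.

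**Conclusion.** The point holds as a minor, low-cost improvement. The over-time MMRM constrains the baseline slope to be equal at all visits. If the true slopes differ, its visit-specific treatment differences, including the Month 12 row, are somewhat less precise than they could be. Under the assumed slopes the Month 12 variance is roughly 1-14% higher for IOP and 2-20% higher for drop count. The drop-count range assumes spread that grows after surgery; with equal spread it is 1-9%. With equal slopes the loss is zero.

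Two stronger conclusions are not supported. The trial's Month 12 comparison as a whole is not weakened, because the single-timepoint change endpoints and the primary endpoint do not use this model. Nor is the estimate biased: randomisation protects it with complete data, and the simulation agrees. Behaviour under dropout was not examined, so no claim is made about it.

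**What to change.** In SAP 5.4.2.1, add a baseline-by-time interaction to the over-time MMRM for both IOP and number of topical medications, including the analysis in eyes with medicated baseline IOP of 18 mm Hg or less. In the same edit, state the covariance structure and the visits that enter the model, and clean up the sentence so that the endpoints it covers are explicit.

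The cost is one model term and no new data. Eight slopes replace one, so 8 − 1 = 7 further degrees of freedom are used. That is small with about 100 eyes, though it buys nothing if the slopes turn out equal.

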5.4.3. Multiplicity Adjustment

Not applicable.

5.5. Tertiary/Exploratory Endpoint(s) Analysis

The time to complete success and the time to qualified success were added to further explore the timing of achieving complete success or qualified success with the treated eyes. If the patients haven't achieve the 'event' (complete success or qualified success) prior to study completion or study withdrawal, the last known date in the study will be used and the situation will be treated as censored in the statistical analysis.

Kaplan-Meier (KM) analysis will be performed on the time to complete success and the time to qualified success. The median, 25% percentile and 75% percentile will be reported.

5.6. Safety Analyses

Safety analyses will be employed using Safety population.

For ocular safety assessment, analyses will be performed by treatment group including both eyes if both eyes are qualified.

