### **8.3 Selection of Study Population**

#### **8.3.1 Number of Planned Subjects**

This study will include subjects with glaucoma poorly controlled on topical therapy including those who may have had prior SLT or MIGS surgeries who meet the inclusion and exclusion criteria. Any questions regarding a subject's eligibility should be discussed with the sponsor prior to enrollment.

This study plans to enroll subjects at approximately 25 to 40 sites in the United States. A total of approximately 285 subjects will be included in the study: approximately 190 subjects in the XEN arm and 95 subjects in trabeculectomy arm. One eye per subject will be enrolled into the study. This includes an estimated 10% dropout rate after screening (see [Section 11.2](#) for the calculation of sample size).

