### 8.3.2 Inclusion Criteria

To be eligible for study entry subjects must satisfy all of the following criteria in the study eye (only 1 eye will be allowed in the study):

1. Male or female subjects ages  $\geq 18$  years
2. Able to provide signed written informed consent
3. Glaucoma in which the IOP is not controlled on current topical IOP-lowering glaucoma medication
4. Best-corrected baseline Snellen visual acuity of 20/100 or better
5. Visual field mean deviation no worse than -18.0 dB (with no dense paracentral scotomas, eg,  $>18$  dB total deviation on 1 or more of the 4 paracentral points)
6. Medicated IOP  $\geq 15$  mm Hg and  $\leq 44$  mm Hg on at least 1 topical IOP-lowering medication
7. Subjects not anticipated to require any other ocular surgery (eg, cataract surgery) in either eye up to 3 months from the time of inclusion
8. Area of healthy, free, and mobile conjunctiva in the target area, ie, superior bulbar conjunctiva
9. Visible trabecular meshwork with Shaffer angle grade  $\geq 2$  in the target area or, in eyes with prior failed angle surgery, an open angle in the target area
10. Preoperative laser trabeculoplasty is allowed 3 or more months prior to randomization
11. Failed ab-interno canal or suprachoroidal MIGS procedures (such as i-Stent®, gonioscopy-assisted transluminal trabeculotomy [GATT], ab-interno canaloplasty [ABiC™], Kahook Dual Blade goniotomy, etc) are allowed 3 or more months before enrollment, with the exception of CyPass® Micro-Stents, which are not allowed. Ab-interno ablative procedures (such as endoscopic cyclophotocoagulation [ECP]) are also allowed 3 or more months before enrollment.

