### **11.1.1 Datasets or Populations Analyzed**

The Enrolled population consists of all study eyes for which the subject has signed the ICF. The Enrolled population will be used to summarize disposition data.

The Intent-to-treat (ITT) population consists of all enrolled eyes randomized to study glaucoma surgery (XEN or trabeculectomy). The ITT population will be the primary analysis population for effectiveness data. Subject demographics, baseline characteristics, and PRO data will be analyzed using the ITT population. Subjects will be grouped and analyzed according to the actual surgery received.

The Modified Intent-to-treat (mITT) population consists of eyes in the ITT population that receive study glaucoma surgery and have no major protocol deviations, which will be defined in the SAP and identified prior to database lock. The mITT population will be used for selected effectiveness endpoints (as specified in the SAP), and will be used for the analyses of PRO data also.

The Safety population consists of all enrolled eyes that undergo study glaucoma surgery, whether surgery is completed or aborted, and have follow-up visits or evaluations. The Safety population will be used to analyze AEs, medical and ophthalmic history, and concomitant medications (ocular and systemic). Subjects will be grouped and analyzed according to the surgery they received.

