Participants will be randomized in 2:1 ratio, resulting in approximately 68 eyes being implanted with XEN and approximately 34 eyes receiving trabeculectomy. Participants will be screened for enrollment, and eligible candidates will be approached to ascertain interest in study participation. Study duration will be approximately 12 months, and Table 1-1 shows the schedule of assessment.

If both eyes meet the inclusion criteria, the investigator will determine the study eye. And only the study eye will be treated with the randomized treatment.

CONFIDENTIAL
XEN-45 Gel Stent

Table 1-1 Schedule of assessment

Procedure / Data to be Recorded	Baseline Qualifying Visit ^a	Preoperative Visit 1 ^a	Operative		Postoperative Visits (visit window; time since Day 0)															
			Visit 2 Day 0	Visit 3 Day 1 (6-48 h)	Visit 4 Week 1 (3-10 d)	Visit 5 Week 2 (11-20 d)	Visit 6 Month 1 (3-8 wk)	Visit 7 Month 3 (9-17 wk)	Visit 8 Month 6 (18-32 wk)	Visit 9 Month 9 (33-47 wk)	Visit 10 Month 12 (48-60 wk)									
Demographics	X																			
Medical and Ophthalmic History	X																			
Subject Eligibility	X																			
Informed Consent/HIPAA	X																			
Concomitant Medications and/or Procedures Review	X	X	X	X	X	X	X	X	X	X	X	X	X	X	X	X	X	X	X	X
Intraocular Pressure (IOP)	X ^b	X	X	X	X	X	X	X	X	X	X	X	X	X	X	X	X	X	X	X
Autorefractor		X							X			X			X					X
Visual Acuity (BCVA) ^c	X	X	X	X	X	X	X	X	X	X	X	X	X	X	X	X	X	X	X	X
Manifest Refraction	X																			X
Biomicroscopy (slit lamp exam)	X	X	X	X	X	X	X	X	X	X	X	X	X	X	X	X	X	X	X	X
Gonioscopy Assessment (Schaffer's Scale) ^d	X				X ^d															X ^d
Visual Field Exam	X ^e														X					X
Ophthalmoscopy		X	X	X	X	X	X	X	X	X	X	X	X	X	X	X	X	X	X	X
Pachymetry		X	X	X	X	X	X	X	X	X	X	X	X	X	X	X	X	X	X	X
Topography ^f		X	X	X	X	X	X	X	X	X	X	X	X	X	X	X	X	X	X	X
Biometry ^f		X	X	X	X	X	X	X	X	X	X	X	X	X	X	X	X	X	X	X
AS-OCT ^f		X	X	X	X	X	X	X	X	X	X	X	X	X	X	X	X	X	X	X
Bleb Photography ^f		X	X	X	X	X	X	X	X	X	X	X	X	X	X	X	X	X	X	X
PRO: SHPC-18 ^g	X		X	X	X	X	X	X	X	X	X	X	X	X	X	X	X	X	X	X
PRO: Postsurgical Question ^g																				
PRO: WPAI ^g	X			X																X
Randomization		X																		
Glaucoma Surgery				X																

CONFIDENTIAL

Statistical Analysis Plan V2.0 |

XEN-45 Gel Stent

	Baseline Qualifying Visit ^a	Preoperative Visit 1 ^a	Operative		Postoperative Visits (visit window; time since Day 0)																

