SAS PROC POWER with the case of TWOSAMPLEFREQ is employed to yield a total sample size of 102 completors (68 in XEN and 34 in Trab). As a result, the study requires to enroll a minimum of 114 patients (76 in XEN and 38 in Trab) in order to achieve the study goal when 10% dropout rate is taken into account.

CONFIDENTIAL

Draft Statistical Analysis Plan v2.0

XEN-45 Gel Stent

4. Populations for Analysis

The analysis populations will consist of participants as defined below:

- **Enrolled population:** For all study eyes for which subjects have signed ICF and met all inclusion/exclusion criteria.
- **Intent-to-Treat (ITT) population:** all enrolled eyes randomized to study glaucoma surgery (XEN or trabeculectomy), and received study glaucoma surgery (XEN or trabeculectomy).
Note that analyses will be based on the randomized surgery.
- **Safety Population :** All enrolled eyes that have undergone study glaucoma surgery.
Note that analyses will be based on the actual surgery treated.

Due to the nature of Phase 4 study, there will be no mITT population to be implemented, unless there are significant protocol deviations or other reasons.

CONFIDENTIAL

Draft Statistical Analysis Plan v2.0

XEN-45 Gel Stent

5. Statistical Analyses

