5.6.2. Adverse Events

Adverse events will be coded by system organ class (SOC) and preferred term (PT) using the Medical Dictionary for Regulatory Activities (MedDRA), version #21.0 or newer.

Adverse events will be classified to either ocular AEs or nonocular AEs. An ocular AE will be determined as indicated on the AE form of eCRF, and thus are not limited to AEs with primary SOC of eyes. The adverse events will be also classified to either AE or adverse device effect (ADE). The summary of AEs will be separately done for nonocular AEs, ocular AEs and ADEs. Ocular AEs and ADEs will be tabulated by treatment group for the study, and nonocular AEs will be summarized by treatment group for participants. eye

An AE will be considered a treatment emergent adverse event (TEAE) if the AE began or worsened (increased in severity or became serious) on or after the date (and time, if known) of the surgery.

An TEAE and ADE will be considered a TESA or SADE if it meets any SAE criterion.

Overall summary of TEAEs will be provided for categories of all TEAEs, treatment-related TEAEs/TEADEs, TESA/TEADE, deaths, TEAEs/TEADEs leading to study discontinuation, TEAEs/TEADEs, treatment-related TEAEs/TEADEs, TESA/TEADEs and TEAEs/TEADEs leading to study discontinuation will be further classified into ocular and nonocular subcategories.

The number and percentage of participants reporting TEAEs/TEADEs in each treatment group will be tabulated by SOC in descending frequency order of XEN first, then by preferred term in descending frequency order of XEN, and further categorized by severity. If more than 1 AE/ADE is coded to the same preferred term for the same participant, the participant will be counted only once for that preferred term using the greatest severity and strictest causality for the summarization by severity and causal relationship.

The number and percentage of participants with treatment-related TEAEs/TEADEs will be tabulated by SOC and preferred term.

Summary tables will be provided for participants with TESA and participants with TEAEs/TEADEs leading to discontinuation. Listings of all AEs, SAEs, and AEs leading to discontinuation by participant will be presented.

The same analysis will be repeated for ocular TEAEs/TEADEs, ocular TESA/TEADEs.

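### SAP Section 5.6 admits both eyes to ocular safety analyses, which contradicts the one-eye design and the Safety population and leaves some outputs open to unoperated eyes

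*SAP*

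**What the plan says.** SAP Section 5.6 opens with two sentences. The first sets the population: "Safety analyses will be employed using Safety population". The second sets the unit for ocular data: "For ocular safety assessment, analyses will be performed by treatment group including both eyes if both eyes are qualified".

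Other parts of the plan point to a single eye per subject:

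- Protocol Section 8.3.1: "One eye per subject will be enrolled into the study". Protocol Section 8.3.2 says the same among the entry criteria: "only 1 eye will be allowed in the study".
- SAP Section 1 covers the case where both eyes meet the inclusion criteria. The investigator chooses one, "And only the study eye will be treated with the randomized treatment".
- SAP Section 4 defines the Safety population by eye: "All enrolled eyes that have undergone study glaucoma surgery". Protocol Section 11.1.1 also requires surgery on the eye: "The Safety population consists of all enrolled eyes that undergo study glaucoma surgery, whether surgery is completed or aborted, and have follow-up visits or evaluations".
- SAP Sections 5.6.3.2 to 5.6.3.5 (biomicroscopy and ophthalmoscopy, BCVA, visual field, pachymetry) each name the study eye.
- SAP Section 5.6.2, on adverse events, reads: "Ocular AEs and ADEs will be tabulated by treatment group for the study, and nonocular AEs will be summarized by treatment group for participants. eye". The final word looks displaced by text extraction. The intended unit for ocular events is probably the study eye.

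**The concern.** The SAP never says what makes an eye qualified. The closest parallel is SAP Section 1, where both eyes may meet the inclusion criteria. That is exactly the situation in which the second eye is not operated on. On that reading, Section 5.6 assigns an unoperated eye to a surgical arm.

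On the other reading, qualified means belonging to the Safety population. Then no subject can contribute two eyes and the sentence never applies. A programmer has to decide whether it is dead text or an exception to the population definition.

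Comparing safety is part of the study's single stated objective. An unoperated eye carries no surgical risk from the study procedure, so counting it under XEN or trabeculectomy either dilutes the rate or attributes events to an operation that the eye did not have.

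**Working it through.** **Step 1: which outputs are exposed.** SAP Section 5.1 sets the study eye as the default for efficacy only, so Section 5.6 holds the only general eye rule for safety.

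| Safety output | SAP section | Eye named? |
|---|---|---|
| Ocular AEs and ADEs | 5.6.2 | Apparently the study eye; participants counted |
| AEs of special interest | 5.6.2.1 | No |
| Eyes with IOP of 6 mm Hg or less | 5.4.2 | No; worded by eye |
| Clinical hypotony | 5.6.3.1 | No |
| Biomicroscopy and ophthalmoscopy | 5.6.3.2 | Study eye |
| BCVA | 5.6.3.3 | Study eye |
| Visual field | 5.6.3.4 | Study eye |
| Pachymetry | 5.6.3.5 | Study eye |

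Three outputs name no eye. SAP Section 5.3.1 describes IOP readings taken for each eye, so fellow-eye pressures may be available to include.

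**Step 2: size of the effect.** The documents give no complication rate and no eye-level safety denominator, so there is no plan figure to reproduce. The rates below are assumptions for illustration. Arm sizes are the 76 XEN and 38 trabeculectomy participants in SAP Section 3.

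Let p be the study-eye rate, q the fellow-eye rate, and f the share of subjects whose fellow eye is added.

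*Eyes as denominator:* rate = (p + f·q)/(1 + f). With q = 0:

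| f | XEN eyes | Trabeculectomy eyes | p = 10% | p = 20% | Difference |
|---|---|---|---|---|---|
| 0 | 76 | 38 | 10.0% | 20.0% | 10.0 points |
| 0.5 | 114 | 57 | 6.7% | 13.3% | 6.7 points |
| 1 | 152 | 76 | 5.0% | 10.0% | 5.0 points |

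The lowest possible value is p/2, reached only at f = 1 and q = 0. With f = 1 and q = 2%, 10% becomes (0.10 + 0.02)/2 = 6.0%. The differences shown assume the same f in both arms.

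*Participants as denominator*, which is what SAP Section 5.6.2 uses for the TEAE tables: rate = 1 − (1 − p)(1 − f·q), treating the two eyes as independent for illustration. With p = 10%:

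- q = 0, any f: 1 − 0.90 × 1 = 10.0%, unchanged.
- q = 2%, f = 0.5: 1 − 0.90 × 0.99 = 10.9%.
- q = 2%, f = 1: 1 − 0.90 × 0.98 = 11.8%.

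**Step 3: the written population.** If the Safety population is applied as defined, f = 0 and every rate equals p.

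**The case against.** The strongest reply is that the plan already excludes unoperated eyes. The sentence immediately before the disputed one sends all safety analyses to the Safety population, and both documents define that population by operated eyes. A fellow eye is neither enrolled nor operated on. The sentence is also conditional, and nothing in Section 5.6 says that qualified means meeting entry criteria. The specific subsections name the study eye, and specific text normally takes precedence over general text.

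Most of this stands, and it rules out a stronger reading that is tempting. A reader might infer that untreated fellow eyes will dilute complication rates across the safety results. The documents do not support that. Dilution needs both the admission of unoperated eyes and an eye-level denominator. The TEAE tables count participants, where an added eye cannot lower a rate.

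A reader might also object that two eyes of one person would be treated as independent. That has little consequence here: safety results are counts, percentages and descriptive summaries, with no planned safety test or confidence interval that within-person correlation could invalidate.

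The reply does not remove the contradiction. If the population definition governs, the sentence can never apply, yet it stands as an instruction. SAP Section 5.3.1 does identify hypotony by patient, but that does not say which eye counts, and the other two outputs in Step 1 have no study-eye wording to fall back on.

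**Conclusion.** The point holds as an internal contradiction with an undefined term, with a limited possible effect on three safety outputs. If the Safety population is applied as written, there is no numerical effect. If the sentence is applied literally, an eye-level rate falls by at most half in an arm, under the extreme assumption that every fellow eye is added and has no events. Participant-level rates stay the same or rise, and the harm there is misattribution. The event rates and qualifying shares used are assumptions, not figures from the documents.

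The primary analysis is not touched, because efficacy is restricted to the study eye. Table specifications are held in a separate document that was not available, and they may already settle the unit. The correction is worth making because a stated rule conflicts with the design, but it is modest in weight.

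**What to change.** Replace the second sentence of SAP Section 5.6 with: *Ocular safety analyses are performed on the study eye in the Safety population by treatment group; fellow-eye events are listed separately.*

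This agrees with the one-eye design, the Safety population definition and the study-eye subsections. It also settles which eye counts for clinical hypotony, low IOP and the events of special interest, while keeping fellow-eye events visible. The cost is one SAP sentence and a check that the separate table specifications agree. No new data are needed.
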